6.3 Characterization of treatment response

The two centers will use identical clinical criteria of diagnosis of cNF which is a clinical diagnosis made in a person with NF1 who has skin neoplasms involving the dermis (see Fig. 1).

The cNFs to be treated will initially be described relative to anatomical site, tumor size at baseline, cNF subtype (Fig. 1), pigment, hair, and associated symptoms and signs at the time of treatment. The rationale for selection of tumors will be described (pain, itch, disfigurement). The selected tumors will be documented by 2D and 3D photos.

The centers will furthermore use two different methods to document the base-line state of the selected cNFs, and the response and result of the treatment immediately after treatment, and in the subsequent follow-up visits. Each method is well established in the respective department routine. In addition to the digital images, in Denmark cNF will be measured with 20 MHz pulsed ultrasound imaging and in Sweden a selection of cNF tumors will be biopsied (see section 6.2 and 6.3.2).

6.3.1 Denmark - High-frequency ultrasound cross-sectional ultrasound imaging.

In Denmark, measurements of the baseline state of cNFs to be treated, and subsequent response to the treatment will be based on 20 MHz pulsed ultrasound imaging.

20 MHz ultrasound assessment has been used in many fields in dermatology for measurement of skin and tumor thickness and for characterization of inflammatory skin diseases since its introduction in 1979. Tumors and inflammation create low echogenic vertical profiles in the dermis, which can be measured by ultrasound imaging, including an analysis of the image density registered as low echogenic pixels (27).

The DermascanC, from Cortex Technology, Hadsund, Denmark will be used. Ultrasound imaging assessment with this system creates real-time, cross-sectional images to a depth of up to 4 mm with axial resolution about 25 μ m and lateral resolution about 70 μ m. The ultrasound pulses are of low energy and involves no safety concerns related to persons being scanned, and has no therapeutic effect confounding the HIFU treatment.

Scanning is non-invasive and not associated with any pain or discomfort. In this study the manual method of recording in vivo distances and thickness will be applied, and not the automatic facility having less accuracy (27). An example of an ultrasound imaging of a dermal tumor (not cNF) with qualitative measurement of the cross-sectional area is shown in Fig. 5.

[figure not shown]

Fig. 5. Example of measurement of a tumor cross-section using the Cortex DermaScan C device (not cNF). Source: https://cortex.dk/scientific-ultrasound-dermascan-c/

Ultrasound imaging assessment will be performed on all treated and control cNFs included in the evaluation at baseline (visit 2), one week after treatment (visit 3), 12 weeks after treatment (visit 4), 24 weeks/6 months (visit 5) and 39 weeks/9 months (visit 6). This will be done concurrent with 2D and 3D photos (Table 1).

6.3.2 6.3.2 Sweden – Biopsy

In Sweden, patients will undergo biopsy of a minimum of 3 cNFs (1 control/reference, 1 cNF biopsied one week after treatment, and 1 cNF at 12 weeks after treatment) and a maximum of 7 (1 control and 6 treated cNF) to characterize the baseline and treated response at two time points (1 and 12 weeks after treatment) (**Fig. 6**).

The control biopsy will be taken one week after the treatment (visit 3). Biopsies of the treated tumors will be taken one week after treatment (visit 3) and 3 months after treatment (visit 4). The pathologic analysis of these tumor samples will illustrate the short-term inflammatory response and mid-term healing effects respectively. If the patient is willing to have more tumors treated and biopsied, a maximum of 1 control biopsy and up to 6 biopsies from treated tumors per patient will be taken throughout the study. The schedule for biopsy characterization is illustrated in Fig. 6.

Tumors subject to biopsy are lost for clinical follow up, thus, up to nine lesions per patient will preferably be included in the study in the Swedish center. cNFs selected for biopsy must be 2-5 mm in diameter. Biopsy is preferably taken as a punch biopsy, but the investigator may decide to perform a surgical biopsy or a shave biopsy depending on participant's preference and the aim to possibly remove the entire lesion with the biopsy.

The tissue collected via biopsy will be assessed with standard histology and immunohistochemistry.

[figure not shown]

Fig 6. Schema for cutaneous neurofibroma biopsies.

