Photo documentation 3D		X1	х	х	х	x
Ultrasound Imaging Assessment (Bispebjerg Hospital)		X1	х	х	х	x
HIFU treatment		X2				
Participant questions and scoring		X1	х	х	х	x
Medical team questions and scoring		X1	х	х	х	x
Adverse Event Reporting		X1	х	х	х	x
Biopsy of 1-3 treated cNF ³ (Sahlgrenska Sjukhuset)			х	х		
Biopsy of 1 untreated cNF (Sahlgrenska Sjukhuset)			х			

1 = Data collection should occur immediately before treatment and again within one hour after treatment

2 = A minimum of 5 cNF 2-5 mm in size are required for enrollment. A minimum of 3 and a maxumum of 9 cNF will be treated and assessed across visits 2-6

3 = The minimum number of cNF to be biopsied is 3 (two treated and one control). The maximum number of cNF to be biopsied is 7. The biopsies will occur for cNF that are between 2-5 mm in size at visits 3 and 4. There will be one untreated cNF biopsied at visit 3. A minimum of one treated cNF will be biopsied at both visit 3 and visit 4.

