5.2 Secondary endpoints – Efficacy, safety and feasibility

- Efficacy: Rate of clearance, e.g. reduction of tumor mass of treated cNFs based on 2D and 3D photography or ultrasound imaging assessment at 3 and 9 months parallel to assessment of the degree of dyspigmentation with hypermelanosis or hypomelanosis of the lesion and the perilesional untreated skin.
- Safety: Itch and pain from the treatment measured on a 0-10 point numerical scale.
- Safety: Wheal and flare reaction and inflammatory responses are measured on a graded scale.
- Safety: Any objective adverse effect or event, local or systemic, related to the treatment and the investigational device is measured (wound and course of wound healing, scar formation, instrumental hazards) is categorized immediately after treatment and at all follow-up visits.
- Feasibility: Feasibility is evaluated both quantitatively (time spent on treatment) and qualitatively depending on the object considered and cover elements that may compromise or favor HIFU relative to other treatments employed for lesions in clinical practice or from the literature. Feasibility assessment will not produce a direct comparison with alternative methods since the study has no arm with an alternative method. The evaluation comprise the following essentials:
 - 1) Time and resource spent on the treatment session using the device,
 - 2) Investigators' assessment of the practice of using the device and the treatment,
 - 3) Participants" assessment of satisfaction with the treatment and the device.

All skin toxicities will be grated according to the classifications in Common Terminology Criteria for Adverse Events (CTCAE), U.S. Department of health and human services, Ver 5.0, Nov 27, 2017.

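### No rule fixes which Swedish treated tumours are biopsied, or when they are chosen, so the 9-month Swedish clearance and regrowth results can be biased

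*Combined protocol and SAP*

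**What the plan says.** Efficacy is a secondary endpoint (Section 5.2): "reduction of tumor mass of treated cNFs based on 2D and 3D photography or ultrasound imaging assessment at 3 and 9 months". Section 5 adds registration of regrowth at 6 and 9 months.

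In Sweden, treated tumours are biopsied after treatment, at visit 3 (one week) and visit 4 (12 weeks). Table 1 gives "Biopsy of 1-3 treated cNF" at each of these visits, and its footnote 3 adds: "A minimum of one treated cNF will be biopsied at both visit 3 and visit 4". Section 6.3.2 caps treated biopsies at six per participant and states the consequence: "Tumors subject to biopsy are lost for clinical follow up".

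On selection, Section 6.2 has the study tumours chosen and documented at visit 2. It says the CRF will identify the control tumour and the treated and sampled tumours. It does not say when the sampled ones are named, or how.

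On size, Section 6.3.2 says "cNFs selected for biopsy must be 2-5 mm in diameter" without a time point. Footnote 3 mentions the same range together with visits 3 and 4. Section 6.1 describes the study as open-label.

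**The concern.** Once a tumour is biopsied it no longer contributes to follow-up, so the 9-month clearance rate is computed on whatever was not taken. If the choice is independent of response, this costs only precision. If it depends on response, the remaining tumours are a selected group.

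Two features of the plan leave that open. First, by week 12 the investigator and participant can see which tumours have responded. Second, if the 2-5 mm limit in footnote 3 applies on the day of biopsy, a tumour that has shrunk below 2 mm cannot be taken and one that has not shrunk can. Removal would then be tied to response by the wording itself.

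Taking persisting tumours makes 9-month clearance look too good. Taking cleared sites makes clearance look too poor and regrowth too frequent. In either case the 3- and 9-month rates describe different sets of tumours, so a change between them cannot be read as regrowth or continued clearance.

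**Working it through.** **Inputs from the documents.** 10 participants per centre (Section 6.5.6). 3 to 9 treated tumours per participant (Table 1 footnote 2, Section 6.2). 1 to 3 treated biopsies at each of visits 3 and 4 in Sweden (Table 1). No biopsies in Denmark. The plan gives no expected clearance rate, so the rates and selection strengths below are assumptions.

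**Step 1: attrition.** At the minimum, 3 - 1 = 2 tumours remain after week 1, and 2 - 1 = 1 after week 12. This reproduces the minimum flow of 3, 2, 1 in Fig. 2. Over 10 Swedish participants, 30 treated tumours become 20 and then 10, so 20/30 = 67% are lost before 9 months. With 9 treated and 3+3 biopsied, 9 becomes 6 and then 3, again 67%. With 9 treated and 1+1 biopsied, the loss is 2/9 = 22%.

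**Step 2: bias at 9 months, minimum numbers.** Assume the week-1 choice is unrelated to response and tumours respond independently. Let r be the true clearance rate. Let q be the probability that the uncleared tumour is taken at week 12 when one of the remaining two is cleared and the other is not. The surviving tumour is cleared with probability

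s = r² + 2r(1 - r)q.

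With q = 0.5 (choice unrelated to response), s = r² + r(1 - r) = r, so there is no bias. If an uncleared tumour is three times as likely to be taken, q = 3/4. If it is always taken, q = 1. The rate pooled by tumour with 30 unaffected Danish tumours is (30r + 10s)/40.

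| True r | Sweden, q = 0.75 | Sweden, q = 1 | Pooled, q = 0.75 | Pooled, q = 1 |
|---|---|---|---|---|
| 30% | 0.09 + 0.42 × 0.75 = 40.5% | 51% | 32.6% | 35.3% |
| 50% | 0.25 + 0.50 × 0.75 = 62.5% | 75% | 53.1% | 56.3% |
| 70% | 0.49 + 0.42 × 0.75 = 80.5% | 91% | 72.6% | 75.3% |

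**Step 3: opposite direction.** At r = 50%, if the cleared tumour is three times as likely to be taken (q = 0.25), s = 0.25 + 0.125 = 37.5%. If it is always taken (q = 0), s = 25%. Pooled, these give (15 + 3.75)/40 = 46.9% and (15 + 2.5)/40 = 43.8%.

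**Step 4: correlation within participant.** With an assumed correlation of 0.3 and r = 0.5, both remaining tumours are cleared with probability 0.25 + 0.3 × 0.25 = 0.325. Exactly one is cleared with probability 0.5 × 0.7 = 0.35. With q = 1 the Swedish rate is 0.325 + 0.35 = 67.5%, down from 75%.

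**Step 5: more treated tumours.** With 9 treated, 1+1 biopsied, r = 0.5 and an uncleared tumour always taken at week 12, 8 remain after week 1. A cleared tumour is taken only if all 8 are cleared. The rate is (8 × 0.5 - 0.5⁸)/7 = 57.1%. With 3+3 biopsied, 6 remain after week 1 and 3 after week 12. The expected number cleared is (1 × 6 + 2 × 15 + 3 × 42)/64 = 2.53, and 2.53/3 = 84%. What matters is the share removed at week 12 (1 of 8 against 3 of 6).

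**Step 6: the 3-month rate.** Fig. 2 still shows at least two treated tumours at month 3, and Table 1 schedules photographs at visit 4. A tumour biopsied at visit 4 therefore counts at 3 months, provided its images are taken and used before the biopsy; Table 1 does not give the order. The other route is the week-1 biopsy, which biases the 3-month rate only if the early reaction predicts later clearance.

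**The case against.** The strongest reply is that advance selection may be intended. Section 6.3 refers the reader to Section 6.2 for the biopsied tumours, and Section 6.2 opens with selection at visit 2. Table 4 lists biopsy monitoring from visit 2, although none is taken then. Fig. 6, the biopsy schema, is not available to us. This stands as a possibility: the documents do not show that the choice is left until the response is seen. They also do not say that it is made earlier, and stating so would cost one sentence.

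Several stronger readings are tempting but not supported:

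- A reader might infer from "the aim to possibly remove the entire lesion with the biopsy" and the accompanying mention of participant preference that these govern which tumour is taken. In Section 6.3.2 they govern the technique (punch, surgical or shave). Footnote 3 is the better evidence.
- A reader might infer that the 3-month rate, and with it the 20% termination criterion in Section 6.5.5, is equally at risk. Step 6 shows two narrow routes only.
- A reader might infer that the survivors drift towards larger tumours. That needs larger tumours to be treated as well, and under the biopsy-day reading of footnote 3 tumours below 2 mm are also spared.
- A reader might take 75% as the expected distortion. It requires independent tumours, certain selection and minimum numbers.

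It is also fair that Section 6.3.2 prefers up to nine lesions per Swedish participant because of this loss. That helps if few are biopsied, but not if six are. Finally, clearance is secondary, has no success threshold and plays no part in the sample size, and Danish data are unaffected.

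**Conclusion.** The gap is real: the plan as written permits response-dependent removal of up to two thirds of the Swedish treated tumours before 9 months. Bias is possible rather than shown, and its direction is not certain. It concerns the 9-month Swedish clearance and regrowth results, not the primary tolerability endpoint.

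At a true rate of 50%, three treated tumours, 1+1 biopsied, independent responses and a week-1 choice unrelated to response, Sweden reads 62.5% under threefold preference for uncleared tumours and at most 75% under certain selection. The pooled rate by tumour is about 53% to 56%. Selection the other way gives 25% to 37.5% in Sweden. Within-participant correlation reduces the bias, and so does treating more tumours for the same number of biopsies (about 57% with 9 treated and 1+1 biopsied under full selection). Removing a larger share at week 12 raises it. The plan should be changed on this point, because the information cannot be recovered once tumours have been removed.

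**What to change.** 1. At visit 2, before HIFU, draw at random from the participant's accepted treated tumours which go to the week-1 and which to the week-12 biopsy. Balance over flat, sessile and globular types where possible, and record the allocation in the CRF.
2. State that the 2-5 mm limit used for this allocation is the baseline size, and reconcile Table 1 footnote 3 with Section 6.3.2.
3. At visit 4, take the images and count them in the 3-month result before the biopsy.
4. Report 9-month clearance in never-biopsied tumours, beside the 3-month result for the same tumours.

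The cost is one CRF field and a few sentences of protocol text. The downside is that the participant and investigator have less say over which tumour is sampled. With random allocation the expected rate in the remaining tumours equals the true rate, and only precision is lost: at minimum numbers, 10 of 30 Swedish tumours still carry the 9-month result.

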6.4 Investigational device

The investigational device, TOOsonix System ONE-M, was CE-marked as an electrical medical device according to MDD as a Class I device in July 2020. The device therefore conforms to the relevant safety requirements needed for human treatments in the harmonized IEC standards covering medical devices. Type testing was performed by TÜV SÜD, with a range of supporting evaluations and tests performed by internal and external parties.

The device is indicated for a range of aesthetic procedures, and has furthermore been used in casebased treatments, on the doctor's clinical responsibility, for selected clinical volunteers that could not helped by other treatments.

Recently a GCP clinical Investigation on removal of non-nodular basal cell carcinoma using the device was submitted and conditionally approved by the Danish medical and ethics authorities. The study is planned to start in the autumn 2021 after all final relevant contracts and have been signed.

During operation, the HIFU device is not in contact with the participant except for the touch from the tip of the hand piece held against the skin surface, with a standard ultrasound gel used as coupling medium between skin and probe. There is no electrical contact between device and participant. The contact involves no physical insult, cut or injection, and no breakage of the skin barrier. Probe tip and cables are validated allergen free and biocompatible.

No comparator device is included in the study, and no medicinal product is involved.

6.5 Participants

Study participants are recruited among the hospital patients of the two centers, invited out of the routine offering them different treatment options. Further recruitment may be made by direct referral of eligible patients after contact to other relevant hospital departments and centers or patient associations in these the respective countries.

Diagnosis of their cNF is according to standard routine of the hospitals. Confirmation of the neurofibromatosis syndrome by biopsy is not used in the routine since the disease is characteristic and commonly diagnosed by simple means e.g. history and clinical signs. Patients may have been evaluated genetically or not. Participants' enrolment as hospital patients continues along with their participation in the study.

Because most patients with NF1 and cNF wish many of their cNFs treated, there is no upper limit of number to be treated according to the protocol. The patient and the physician will decide the cNFs to be treated.

6.5.1 Inclusion criteria and selection

- Males and females 18 years of age or older.
- Have a clinical diagnosis of NF1 based on the most recent published criteria (35) (Appendix 2)
- Patients must be seeking active treatment for cNF.
- Patients must have ≥ 5 cNF that are visible and measure a minimum of 2 mm in size. These must be in areas amenable to treatment and surveillance.
- Patients with Fitzpatrick Type I to VI skin-type
- Able and willing to comply with all visits, treatments, evaluations, schedules, and requirements.
- Patients shall have received oral and written study information, accepted participation and signed the informed consent document.
- Patients who are willing and mentally and physically capable to understand and follow the treatment and follow-up schedule including post-treatment care instructions.
- Patients who are willing to have photographs and images taken of the treated lesions to be used anonymously or coded in evaluations and publications.

6.5.2 Exclusion criteria for participant selection (non-inclusion criteria)

- Patients who are undergoing other treatment modalities or investigational agents for their cNF lesions.
- Individuals who cannot give informed consent or adhere to study schedule.
- Patients who are actively tanning during the course of the study.
- Patients with adverse reactions to compounds of any external agent in use.
- Patients with known allergy to injectable anesthetics (relevant for biopsy only).
- Patients with any condition which, in the Investigator's opinion, would make it unsafe (for the participant or study personnel) to treat the participant as part of this research study.
- Patients, where target treatment may cause the acoustic beam to enter the eye.
- Pregnant females, due to possible discomfort with the procedure even though the procedure is localized and there is no new drug.
- Patients with tendency for keloid and hypertrophic scar formation.
- Patients with impaired wound healing.
- Patients with any other acute or chronic condition which, in the opinion of the investigator, could interfere with the conduct of the study.

6.5.3 Criteria and procedures for participant withdrawal or lost to follow up

- Exclusion criteria identical to non-inclusion criteria, however, appearing during the study.
- Patients acquiring disease of higher priority contraindicating their further participation or making participation not possible in practice.
- Patients' decision to leave the trial, irrespective of reason.
- Patients' non-adherence to the study schedule.
- Unforeseen hazards or significant clinical adverse events making continuation of the study not ethical.

6.5.4 Withdrawal from the Study

Each participant has the right to withdraw from the study at any time without prejudice. The investigator may discontinue any participant's participation for any reason, including failure to comply with the protocol (as judged by the investigator such as compliance below 80%, failure to maintain appointments, etc.).

Should a participant withdraw from the study, the reason(s) must be stated on the case report form, and a final evaluation of the participant should be performed.

Patients who go off treatment must be followed for AEs for at least 30 days from treatment or biopsy.

Reason for withdrawal from study is documented in the case report form. Withdrawals after HIFU treatment and before the 3-month visit are replaced and not included in the analysis of results (but registered as dropouts). Withdrawals after 3 months are replaced on investigators discretion.

6.5.5 Study Termination Criteria

The study may be terminated for multiple potential reasons. Some of these reasons include:

• Majority of participants experience severe and unbearable pain, on investigator's decision based on a minimum of 3 participants.

- Unbearable immediate wheal and flare reaction with severe itch and swelling and urticaria disseminating to larger skin areas experienced by a minimum 3 patients, on investigator's decision as indicated above.
- Any systematic (general or local) acute response to the treatment deemed by the investigator to be a clinically significantly different clinical or psychological reaction or adverse event than expected.
- The efficacy of the treatment is in the majority of participants at the 3-month interim assessment (visit 4) deemed to be unacceptably poor by the investigator or the sponsor. Unacceptable efficacy is defined as cure rate below 20% at the 3-month visit, based on a sample of minimum 8 participants in each group of the study.

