Coordinating Clinical Investigator	[name] Chief Physician Ass. Professor, PhD, specialist in dermatology DK MD registration ID: [name] Department of dermatology, Bispebjerg University Hospital [name] Email: [contact]
Principal investigator Denmark	[name] Chief Physician Professor, dr. med., specialist in dermatology DK MD registration ID: [name] Department of dermatology, Bispebjerg University Hospital, [name] Email: [contact] [contact]
Principal investigator Sweden	[name] [name], PhD, specialist in dermatology SE MD registration ID: [name] Department of Dermatology and Venereology, Sahlgrenska University Hospital [name] Email: [contact] [contact]
Investigator Sweden	[name] Chief Physician PhD, Specialist in Dermatology Department of Dermatology and Venereology, Sahlgrenska University Hospital [name]
GCP support Denmark (pending contract)	GCP-enheden ved Københavns Universitetshospital Frederiksberg Hospital [name] E-mail:[contact] Tlf: [name]
GCP support Sweden (pending contract)	Gothia Forum for Clinical Studies Research Support Office Sahlgrenska University Hospital [name] Email: [contact] [contact]

Table 1. Planned activities in the clinical investigation. The investigation consists of a single treatment session (Visit 2) with 3 subsequent follow-up evaluations. The first data analysis and report on primary end-points will be done as an interim assessment after the 3-month visit has been completed by all participants (Visit 4). Primary and secondary end-points are concluded in a final report after all participants have completed the 9-month visit (Visit 5).

Visit number	1	2	3	4	5	6
Event Name	Pre-study	Day 0	7 ± 3 days	12 ± 2 weeks	24 ± 2 weeks	39 ± 3 weeks
			(1 week)	(3 months)	(6 months)	(9 months)
	Consent, Screening and Enrollment	Pre-treatment documentation, treatment, and post- treatment assessments	Evaluation of wound generation	Evaluation of healing and surveillance for any new lesions	Evaluation of healing and surveillance for any new lesions	Evaluation of healing and surveillance for any new lesions
Clinical evaluation	х	x	х	х	х	x
Inclusion and registration	х					
Informed consent	х					
Photo documentation 2D		X1	х	х	х	x

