5.1 Primary endpoint - Tolerability

- The grade of any adverse events (AE) requiring medical intervention within three months of treatment should be low. Device-based treatment will be considered tolerable if less than 30% of participants treated have an "Overall AE Score" larger than Grade 2 AE at the 3month follow-up (visit 4) as assessed via Common Terminology Criteria for Adverse Events (CTCAE), U.S. Department of health and human services, Ver 5.0, Nov 27, 2017.
- The rate and nature of spontaneous healing of the treated cNF lesion and any safety related event including potential wound formation and wound healing should be equivalent to expectations from alternative method(s). Safety evaluation includes rating of treatment associated sequele by end of study, e.g. dyspigmentation and scarring and overall investigator rating compared to expectations.

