Clinical recording of the study includes clinical assessment of healing and therapeutic effect on the tumors. Such assessment follows clinical criteria described in textbooks, guidelines and clinical consensus in the specialty of dermatology. Prior to study, the two investigator sites have coordinated their clinical assessment method.

The chosen 9-month total study period is considered acceptable for observation of tolerance and curative effect of HIFU for cNF with observation of primary therapeutic effect after 3 months. Assessments includes monitoring of the wound healing phase, observation of late recurrences, and observation of scarring.

The study includes no follow up medication, but the study can involve use of wound healing dressings and other remedies in the wound healing phase on investigators individual recommendation. The study involves no standard recommendation on post treatment care, which is anticipated to be simple.

After the study participants are followed in the respective hospital departments according to their needs and the department routines.

Participants who drop out of the study before the 3-month visit voluntarily or for non-medical reasons, including non-adherence, will be replaced by new participant(s). Withdrawals after 3 months are replaced on investigators discretion with considerations to the impact of the overall investigation schedule.

Patient with incomplete cure documented by ultrasound imaging assessment or biopsy and histology after 3 months or subsequent control visit (indicated by clinical suspicion of reoccurrence) will be offered a second treatment based on the standard treatment offered by the center. The specific treatment will be decided by the investigator and the patient based on the extent and severity of the recurrence.

The study will conclude when all participants have completed the 9-month study period, when all data are on file, and the statistical analysis is concluded. Interim analysis of data collected after 3 months and later is allowed, per investigator's decision.

If the study design is deemed inferior, the protocol can be amended.

The study produces no physical test samples relevant for purposes outside the study.

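### Section 6.5.3 turns every entry exclusion into a withdrawal criterion after the single HIFU session, so follow-up can end because of healing problems under study or the second treatment that 6.6 offers

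*Combined protocol and SAP*

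**What the plan says.** - **Withdrawal rule.** The first bullet of 6.5.3 is "Exclusion criteria identical to non-inclusion criteria, however, appearing during the study". It makes no exception for events that follow HIFU.
- **What it imports.** The list in 6.5.2 includes "Patients with impaired wound healing", "Patients with tendency for keloid and hypertrophic scar formation" and "Patients who are undergoing other treatment modalities or investigational agents for their cNF lesions".
- **Exposure.** The Table 1 caption says "The investigation consists of a single treatment session (Visit 2) with 3 subsequent follow-up evaluations". The table itself lists four post-treatment visits, the last at 39 weeks. Swedish participants also have study biopsies at visits 3 and 4.
- **Outcomes.** Section 5.1 counts wound formation and healing in the primary tolerability assessment and adds: "Safety evaluation includes rating of treatment associated sequele by end of study, e.g. dyspigmentation and scarring". Section 5.2 has the course of healing and scar formation categorised at every follow-up visit.
- **Second treatment.** Under 6.6, participants with incomplete cure at 3 months or at a later control visit "will be offered a second treatment based on the standard treatment offered by the center".
- **Handling of withdrawals.** Section 6.5.4 replaces withdrawals between HIFU and the 3-month visit and omits them from the analysis. Later withdrawals are replaced at the investigator's discretion. It asks for a final evaluation and states: "Patients who go off treatment must be followed for AEs for at least 30 days from treatment or biopsy". Section 6.6 limits replacement before 3 months to dropouts that are voluntary or non-medical.

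**The concern.** An exclusion criterion protects people from entering a study that does not suit them. Once the only HIFU session is over, the same criterion prevents no further HIFU exposure. What it can still do is stop observation, and two of its triggers depend on how the treatment went. Impaired healing is a tolerability outcome, and further cNF treatment is what the protocol itself offers after incomplete cure.

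If those participants leave, follow-up depends on outcome. The end-of-study scarring and healing ratings, and the 6- and 9-month regrowth and clearance data, would come disproportionately from participants who healed well and needed nothing more. In an open-label, uncontrolled study of 20 participants, losing a few in this way can change the conclusion.

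**Working it through.** The plan gives no figure for withdrawals. Its sample-size figure reproduces, 1.96² × 0.90 × 0.10 / 0.15² = 15.37, rounded up to 16, but does not depend on this rule. The check is therefore mainly a comparison of sections.

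**1. Impaired healing before month 3.** Healing is an outcome in 5.1 and 5.2. Impaired healing is an exclusion in 6.5.2. Section 6.5.3 makes an exclusion that arises later a withdrawal criterion. Section 6.5.4 then omits the participant from the analysis. Nothing in the protocol breaks this chain.

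**2. Second treatment from month 3.** Section 6.6 offers incompletely cured participants the center's standard treatment. Accepting it fits the 6.5.2 exclusion for other cNF treatment, and so 6.5.3. One section provides for re-treatment; the other makes it a ground for withdrawal. The exclusion is also not limited to study tumors, and 6.5.1 recruits people who are seeking treatment.

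**3. What remains after withdrawal.** A final evaluation, and AE follow-up of at least 30 days from treatment or biopsy. The 3-month visit is at 12 weeks, or 84 days. A Danish participant, who has no biopsy, has already met the 30-day minimum if withdrawn after day 30. No further study visits are required.

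**4. Replacement.** Section 6.5.4 replaces all withdrawals before month 3. Section 6.6 replaces only the voluntary or non-medical ones. A withdrawal for impaired healing is replaced under the first and not under the second.

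**5. Illustration of size (all counts and shares are assumed).** The tolerability rule in 5.1 is below 30% above Grade 2 at 3 months, so at most 5 of 20. Suppose 7 of the first 20 treated participants are above Grade 2 and two of these are withdrawn before visit 4. Any replacements are taken to be event-free.

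| Handling | Rate | Rule met? |
|---|---|---|
| All 20 kept, nobody replaced | 7/20 = 35.0% | No |
| Two omitted and replaced (6.5.4) | 5/20 = 25.0% | Yes |
| Two omitted, not replaced | 5/18 = 27.8% | Yes |
| Two replaced, but all treated participants analysed | 7/22 = 31.8% | No |

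In probability terms, let p be the true rate above Grade 2 and w the share of affected participants withdrawn and replaced. The observed rate is p(1 − w)/(1 − pw). With p = 0.30:

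- w = 0: rate 0.300; chance of at most 5 of 20 is 41.6%.
- w = 0.25: 0.225/0.925 = 0.243; chance 64.4%.
- w = 0.50: 0.150/0.850 = 0.176; chance 87.4%.

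For a scarring or healing event of any grade, 2 of 20 is 10% (exact 95% CI 1.2% to 31.7%). If both participants are omitted before month 3, the result is 0 of 20 (0% to 16.8%) with replacement. Without replacement it is 0 of 18, with upper limit 1 − 0.025^(1/18) = 18.5%.

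These figures apply only to losses before month 3. For later losses the documents give no basis for a number.

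**The case against.** Several stronger readings are tempting, and the documents do not support them.

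- **That affected participants must leave.** Section 6.5.3 lists criteria without saying withdrawal is compulsory, and 6.5.4 gives the investigator permission to discontinue, not a duty. This stands. It weakens the claim without removing it, because the discretion lies with an unblinded investigator who also grades the primary endpoint.
- **That any hypertrophic scar triggers withdrawal.** The scar criterion concerns a *tendency*, which reads mainly as a patient trait. One scar at a HIFU site meets it only if taken as evidence of that trait. The healing and other-treatment criteria apply more directly.
- **That nothing remains to withhold after day 0.** This is wrong for the Swedish center (target 10 of 20), where biopsies follow at weeks 1 and 12. Healing, scarring and anesthetic-allergy criteria still serve a purpose there, so the exclusions should not simply lapse at HIFU.
- **That re-treatment distorts the 3-month tolerability result.** It is offered only at or after that visit, when incomplete cure has already been documented. Later readings of a re-treated tumor would not be clean HIFU results in any case.
- **That post-HIFU pregnancy and tanning show the same bias.** Both are covered by 6.5.3, but neither is an outcome of HIFU, so they do not show outcome-dependent loss.
- **That safety follow-up simply stops.** Thirty days is a minimum. Section 6.5.6 seeks routine clinical follow-up for everyone, section 16 has device-related events followed at the investigator's discretion, and a final evaluation could record a scar. These protect care, but do not keep the participant in study visits or in the analysis.

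It is also fair to say that the plan as a whole intends to observe poor healing: 6.6 monitors it, and section 14.4 treats delayed healing as a potential adverse event. That makes 6.5.3 look like loose drafting, which is a reason to correct it.

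**Conclusion.** The concern holds in a limited form. Section 6.5.3 does not distinguish ending study procedures from ending follow-up. Read literally, it permits removal of participants with impaired healing, and it contradicts the second treatment offered in 6.6. Before month 3, 6.5.4 also takes such participants out of the analysis, under replacement rules that disagree with 6.6. From month 3, scarring, regrowth and clearance data at 6 and 9 months can be lost selectively; no exclusion from analysis is stated for that period.

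The likely direction is in favor of HIFU, but the size is unknown. The tolerability illustrations rest on assumed counts, on withdrawal before visit 4, on omission under 6.5.4 and on the events being above Grade 2. A reader might take the fall from 10% to 0% as an expected effect. It is not: it shows only what the rules would allow.

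**What to change.** 1. In 6.5.3, state that a 6.5.2 criterion arising after HIFU is recorded as an event or deviation and does not by itself end scheduled follow-up or data collection, as long as valid consent continues. That condition covers loss of capacity to consent. Whether further study procedures such as biopsy go ahead remains for the sponsor and investigator to decide.
2. State that all HIFU-treated participants stay in the tolerability and safety analysis, whether or not they are replaced.
3. Reconcile 6.5.3 with 6.6 on the offered second treatment. Limiting the other-treatment criterion to study tumors would not do this, because the second treatment can itself be of a study tumor. Record the date and tumor of any re-treatment so that later readings of that tumor are flagged.
4. Reconcile the replacement rules in 6.5.4 and 6.6.

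The cost is a short protocol amendment and a re-treatment entry in the CRF. It adds no visits to the schedule and does not change the planned 20. The small downside is that participants with post-treatment tanning, pregnancy or other cNF treatment remain in the data set and must be flagged.
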